# **C5.0 Optional Sub-Study at the Vancouver Site**

The modified Pan-Canadian Early Detection of Lung Cancer risk assessment questionnaire (Figure 2) plus an outdoor and domestic air pollution exposure questionnaire (Appendix 1) will be administered to all newly diagnosed lung cancer patients (estimated to be 1,400 patients over two years) who will be attending the Vancouver Cancer Center of the BC Cancer Agency or the Thoracic Surgery Department of the Vancouver General Hospital (VGH). The VGH Thoracic Surgery Unit is one of four thoracic surgery centers for surgical treatment of lung cancer patients in the entire 4.6 million population in British Columbia. From the risk assessment tool, we will determine the relative sensitivity of the PLCOm2012-risk ≥1.51% threshold versus the USPSTF screening criteria to identify lung cancer patients who are ever smokers.

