## 3.0 Study Plan:

- (3.1) Compare the relative sensitivity of the PLCO m2012 ≥1.51% over 6 years lung cancer risk screening threshold versus the USPSTF screening criteria (55-80 years of age who had smoked at least 30 pack-years and former smokers who had stopped smoking for less than 15 years) in newly diagnosed lung cancer patients.
- (3.2) Recruit 8,000 ever smokers between the age of 55 to 80 years from Canada, Australia, Denmark and Italy and prospectively evaluate the sensitivity, specificity and positive predictive value of the PLCOm2012 and USPSTF selection criteria, in two phases:

Phase I – Canada and Australia (4000 participants)

Phase II - Italy and Denmark (4000 participants)

(3.3) Prospectively evaluate the PanCan lung nodule malignancy risk prediction tool and Lung-RADS for management of lung nodules detected by screening LDCT.

**Significance:** This project addresses the important issues of identifying optimal risk selection criteria for LDCT lung cancer screening in the general population as well as the accuracy of the PanCan Lung Nodule Malignancy Risk prediction tool for management of LDCT detected lung nodules.

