**Figure 7. Lung Nodule Management Protocol** 

## C2. Participant Inclusion and Exclusion Criteria

## C2.1 Inclusion Criteria

- Women or men age 55 to 80 years.
- Current or former smokers. A former smoker is defined as one who has stopped smoking for one or more years.
- An estimated 6-year lung cancer risk of ≥1.51% based on the PLCOm2012 risk prediction model
  or ≥ 30 pack-years smoking history (pack-year is defined as number of pack of cigarettes smoked per
  day multiply by the number of years smoked. If a participant stopped smoking for 6 months or more
  and then restarted smoking again, the time will be subtracted from the total duration of smoking in
  0.5-year increments)
- ECOG performance status 0 or 1.
- Capable of providing, informed consent for screening procedures (low dose spiral CT)

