## C2.2 Exclusion Criteria

- Clinical symptoms suspicious for lung cancer e.g., hemoptysis, chest pain, weight loss
- Any medical condition, such as severe heart disease (e.g. unstable angina, chronic congestive heart failure), acute or chronic respiratory failure, home oxygen therapy, bleeding disorder, that in the opinion of the investigator could jeopardize the subject's safety during participation in the study or unlikely to benefit from screening due to shortened life-expectancy from the co-morbidities
- Have been previously diagnosed with lung cancer
- Have had other non-curatively treated cancer outside the lung.
- Pregnancy
- Pneumonia or bronchitis requiring antibiotic treatment within the last 12 weeks
- Unwilling to have a spiral chest CT
- Chest CT within 2 years
- Does not fit into CT scanner table due to gross obesity
- Cannot lie on CT scanning table on the back with arms over the head
- Received chemotherapy or cytotoxic drugs within the last 6 months
- Unwilling to sign a consent

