# C12. Incremental value of including air pollution in the PLCOm2012 lung cancer risk prediction tool to identify high-risk individuals for LDCT screening (Vancouver Site)

A detailed epidemiologic questionnaire (see appendix) will be administered to participants who consent to this optional study. The questionnaire is a modified version of the *Health and Lifestyle Core Questionnaire For Women and Men* (HLCQ) used in the Canadian Partnership for Tomorrow Projects (CPTP). This questionnaire is particularly thorough in collecting data on personal history and family history of cancer, smoking exposure, alcohol consumption and anthropometric measurement. These represent exposures that are active areas of lung cancer prediction research. For example, it is unclear how to optimally code family history of lung cancer in prediction models. Can prediction be improved by including number of family members with lung cancer (or other cancers) and should early age versus older age of onset be included? Personal history of cancer was an important predictor of lung cancer and PLCO analysis suggested that it might be a useful predictor in never-smokers. However, what components of personal history of cancer are important is unclear - which previous cancer types and which cancer treatment(s) are important are yet to be identified. Some of our recent analyses suggested

that very heavy alcohol use might be predictive of lung cancer independent of detailed adjustment for smoking exposure. But this exposure has not been included in any lung cancer risk prediction model to date. Body mass index has repeatedly been found to be inversely associated with lung cancer and has been included in several lung cancer risk prediction models, including all three PLCO models. However, the nature of the relationship is unknown, and if the underlying association can be more optimally measured for prediction is unknown. The PLCO cohort has 88% White, 5.2% Black, 1.9% Hispanic, 3.8% Asian, 0.6% Pacific Islander and 0.25% American Indian. Black race is a predictor in two of the U.S.-based PLCO models. The impact of race/ethnicity on lung cancer risk prediction in the BC population with different minority group is unknown. The proposed study will clarify these and additional relationships and help improve risk prediction.

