Screening Questionnaire Today's Date: Initials: Birth date: Postal Code: ddmmyy Gender: Male Current Age: ∃ Female Race/Ethnicity: Aboriginal (e.g. First Nations, Métis, Inuit)  $\square$ Latin American/Hispanic Ш South Asian (e.g. India, Sri Lanka, Ш Ш Pakistan, Bangladesh) Southeast Asian (e.g. Malaysia, Indonesia, Viet Black (African or Caribbean descent) Ш East Asian (e.g. China, Japan, Korea, Taiwan) Ш West Asian (e.g. Turkey, Iran, Afghanistan) Ш Filipino 1 1 Ш White (European/Middle Eastern/North African) Other ethnic group not listed above Jewish Ш 1) How old were you when you started smoking regularly? years old 2) Are you still smoking now? Yes No 🖂 3) a. Still Smoking Now Yes: if you are still smoking now, were there periods longer than a year when you did not smoke? Yes No No For how many years did you not smoke between starting smoking and now? \_\_yrs b. Still Smoking Now No: Between the time you started smoking and finally quit smoking, were there periods longer than a year when you did not smoke? Yes \( \sigma \) No \( \sigma \) . For how many years did you not smoke between starting smoking and permanently quitting smoking? \_yrs 4) If you are not currently smoking, how old were you when you stopped? years old On average, when you smoke(d), how many cigarettes a day do (did) you smoke? \_\_\_\_ 6) Have you ever been diagnosed with any cancer(s)? Do not include cancers of the skin other than melanoma. Were any of your blood relatives, mother, father, siblings, children, including half-sisters and half-brothers ever diagnosed with lung cancer? Yes 7) What is the highest level of education you have completed? Some college/University University Graduate 8th grade or less 9th grade to 11th grade High school graduate Post graduate/Professional Degree Technical/Vocational School certificate 8) Have you had a chest x-ray within the last three years? (circle one): Yes No No How many: 9) Has a doctor ever told you that you have Chronic Obstructive Pulmonary Disease (COPD), Emphysema or Chronic Bronchitis? Yes 📋 No 🗌 10) Have you had a CT scan of your chest within the last two years? Yes ☐ No ☐ \_\_\_\_ lbs/\_\_\_Kg 11) Current Height: \_\_ in/\_\_\_\_ cm 12) Current Weight: Estimated Lung Cancer Risk Index PLCO PanCan USPSTF

Figure 3. Lung-RADs Classification (http://www.acr.org/Quality-Safety/Resources/LungRAD)

Lung-RADS for nodules at baseline	Findings	Management		

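### In the newly diagnosed patient comparison (3.1/C5.0) only USPSTF carries an age limit and weight is taken at diagnosis, so relative sensitivity mixes the age cap with the risk model

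*Protocol*

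**What the plan says.** Study Plan item 3.1 sets out a comparison, in newly diagnosed lung cancer patients, in these words: "PLCO m2012 ≥1.51% over 6 years lung cancer risk screening threshold versus the USPSTF screening criteria (55-80 years of age who had smoked". A pack-year minimum and a limit on time since quitting complete the USPSTF definition. The age range sits inside the USPSTF definition; PLCOm2012 is given a risk threshold and no age range.

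Section C5.0 carries this out at two Vancouver services. The questionnaire "will be administered to all newly diagnosed lung cancer patients (estimated to be 1,400 patients over two years"). The stated aim is the relative sensitivity of PLCOm2012 versus "the USPSTF screening criteria to identify lung cancer patients who are ever smokers". Ever smoking is the only restriction on who is scored.

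The prospective cohort differs. Item 3.2 recruits at 55-80, and C2.1 requires "Women or men age 55 to 80 years", so both rules are compared inside the same age window.

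The instrument named in C5.0 is the Figure 2 form. It asks current age, whether the person smokes now, and "12) Current Weight". It also asks birth date, ages at starting and stopping, years not smoked in between, and cigarettes per day. C5.0 states no look-back to a date before diagnosis.

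**The concern.** The useful question is which patients each rule would have picked for screening before their cancer was found. Section A1 frames it that way when it cites the share of United States patients who would have met USPSTF had screening been available earlier. Two features of C5.0 pull away from that question.

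First, unequal age limits. Any advantage of PLCOm2012 among patients under 55 or over 80 comes from USPSTF having an age cap, not from the risk model ranking smokers better. A single all-ages ratio cannot separate the two, and it does not line up with the 55-80 cohort.

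Second, weight. C12 says "Body mass index has repeatedly been found to be inversely associated with lung cancer" and that it is in all three PLCO models. C2.2 treats weight loss as a symptom suspicious for lung cancer and excludes such people from screening; C5.0 does not. Weight lost to the cancer can therefore enter the PLCOm2012 score. USPSTF uses age, pack-years and quit time only, so it is untouched.

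At stake is a published head-to-head sensitivity that could overstate how much the risk model itself adds.

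**Working it through.** **Can an age window be borrowed from elsewhere?** No. The 55-80 criterion in C2.1 belongs to the screening cohort, and C2.2 excludes anyone who meets "Have been previously diagnosed with lung cancer", which describes every C5.0 patient.

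**Direction.** Let f be the share of ever-smoking cases outside 55-80, q the share of those who are PLCOm2012-positive, and S_P and S_U the sensitivities within 55-80. Then:

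- PLCOm2012 sensitivity = (1−f)·S_P + f·q
- USPSTF sensitivity = (1−f)·S_U
- ratio = S_P/S_U + f·q / [(1−f)·S_U]

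The second term is never negative, so the ratio cannot move toward USPSTF. The difference in sensitivities changes by f·(q − (S_P − S_U)), so it moves toward PLCOm2012 only if q exceeds the in-age gap.

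**Size.** C5.0 states no sensitivity or power figure, so there is none to reproduce. For illustration I take the C13.1 planning pair, S_P = 94.3% and S_U = 83.8%, which comes from PLCO data. The in-age ratio is 0.943/0.838 = 1.125 and the gap is 10.5 points. Both f and q are assumptions.

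| f | q = 0 | q = 0.3 | q = 0.6 | q = 0.9 |
|---|---|---|---|---|
| 5% | 1.125 | 1.144 | 1.163 | 1.182 |
| 10% | 1.125 | 1.165 | 1.205 | 1.245 |
| 20% | 1.125 | 1.215 | 1.304 | 1.394 |

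Example, f = 20% and q = 0.6: PLCOm2012 = 0.8 × 0.943 + 0.2 × 0.6 = 0.874; USPSTF = 0.8 × 0.838 = 0.670; ratio 1.304, gap 20.4 points.

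**If the rules were equal within 55-80.** Put both at 83.8%. With q = 0.6 the ratio is 1 + f·q/[(1−f)·0.838], which is 1.04, 1.08 and 1.18 at f = 5%, 10% and 20%. Assume also 22% in-age discordance split evenly, and 980 to 1,260 ever smokers (70-90% of 1,400). A two-sided 5% McNemar test (normal approximation) would then reject in favour of PLCOm2012 in about 48-59%, 96-99% and 100% of studies.

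**At-diagnosis values.** The protocol does not say in words that scoring is at diagnosis; this follows from the form. The weight item acts on PLCOm2012 alone, but its size cannot be computed because the model coefficients are not given. Age and quit time act on USPSTF both ways: some patients pass 80 or 15 years since quitting and drop out, while others reach 55 or 30 pack-years and come in.

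**The case against.** The strongest reply is that the age range is a genuine part of USPSTF. A cancer missed because the patient is 82 is a real miss, and section A2 argues from the share of the at-risk population reached. That stands: the all-ages ratio is a legitimate quantity and should be kept. It answers a different question from the 55-80 cohort, so it should not be the only result.

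It can also be said that giving the form to all patients describes data collection. C13.3 uses the same patients, never smokers included, for the air-pollution work. Age is on the form, and a later analysis plan could restrict to 55-80 and recompute age, quit time and pack-years at an earlier date. This largely stands for those items. It does not stand for weight: earlier weight that was never asked cannot be recovered.

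A reader might infer that every at-diagnosis item favours PLCOm2012. The documents do not support that; the age and quit-time drift is mixed and its net direction is not established. A reader might also take the larger ratios above as forecasts. They are not, since neither f nor q is in the documents, and q could be low among patients under 55.

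**Conclusion.** The concern holds in a limited form. As written, 3.1 and C5.0 let patients outside 55-80 add only PLCOm2012-alone positives, so the ratio can shift only toward PLCOm2012 and blends the age cap with the risk model. On the planning pair, 1.125 becomes 1.16-1.30 for an assumed 5-20% of cases out of age with 60% of them PLCOm2012-positive, and stays at 1.125 if none are positive. The direction for the ratio follows from the text; the size rests on those assumed shares.

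Current weight adds a second, unquantified push on PLCOm2012 alone. No net direction is claimed for age or quit time.

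The reach is modest. C5.0 is an optional sub-study at one site, and the powered comparison in item 3.2 and C13.1 is not affected. It nevertheless delivers item 3.1 and bears on objective 1.1, the choice of selection criteria, so the repair is worth making before data are collected.

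**What to change.** - State in 3.1 and C5.0 one reference date before diagnosis (for example 12 months) and score both rules at that date. Age, quit time and pack-years can largely be recomputed from items already on the Figure 2 form.
- Add one question on usual weight at that date to the version of the form given to patients.
- Report relative sensitivity in ever-smoking cases aged 55-80 at that date alongside the all-ages result, and base any comparison with the prospective cohort on the 55-80 result.

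The cost is one added question, a sentence or two of protocol text and a second analysis set. The 55-80 set is smaller: with the assumed 980-1,260 ever smokers, about 931-1,197 remain if 5% are out of age and 784-1,008 if 20% are. Recalled weight will carry some error.

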## **Project Summary**

Background. The cost-effectiveness of a population-based lung cancer screening program with low-dose computed tomography (LDCT) to reduce lung cancer mortality is strongly influenced by the sensitivity and specificity of the selection criteria for screening. Retrospective analysis by [name] and coworkers showed that the PLCOm2012 lung cancer risk prediction model using 7 non-smoking and 4 smoking variables detects 7.6% more lung cancer and samples 8.7% fewer people compared to the US Preventive Services Task Force (USPSTF) screening inclusion criteria based on age and smoking history alone. The sensitivity and specificity of PLCOm2012 versus USPSTF screening criteria to select smokers for lung cancer screening has not been prospectively evaluated in the general population.

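### In the C5.0 case series, the cancer-history question on the Figure 2 form does not leave out the lung cancer under study, which biases relative sensitivity towards PLCOm2012 in that sub-study only

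*Protocol*

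**What the plan says.** C5.0 (protocol, Optional Sub-Study at the Vancouver Site) names the instrument as "The modified Pan-Canadian Early Detection of Lung Cancer risk assessment questionnaire (Figure 2"), together with an air pollution questionnaire, and says it "will be administered to all newly diagnosed lung cancer patients (estimated to be 1,400 patients over two years"). The use made of it is explicit: "From the risk assessment tool, we will determine the relative sensitivity of the PLCOm2012-risk ≥1.51% threshold versus the USPSTF screening criteria", among patients who are ever smokers. This is the comparison listed as Study Plan item 3.1.

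The form is printed under section G, Figure 2. Item 6 reads "Have you ever been diagnosed with any cancer(s)? Do not include cancers of the skin other than melanoma". The form ends with the line "Estimated Lung Cancer Risk Index PLCO PanCan USPSTF", so one set of answers yields both scores.

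The Project Summary describes PLCOm2012 as "using 7 non-smoking and 4 smoking variables" without listing them. C12, in discussing what the PLCO models contain or might contain, states: "Personal history of cancer was an important predictor of lung cancer". The USPSTF rule in Study Plan 3.1 is "55-80 years of age who had smoked at least 30 pack-years and former smokers who had stopped smoking for less than 15 years", with no term for cancer history.

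Neither C5.0 nor Figure 2 says that the index cancer is to be left out, or that answers refer to a date before diagnosis.

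**The concern.** Item 6 suits the people for whom the form was built. Screening recruits have not had lung cancer, because C2.2 excludes anyone with that diagnosis, so a yes means some other cancer. In the C5.0 series the same question has a fixed answer: every patient has been diagnosed with a cancer, namely the one that makes them a case. The outcome then enters one of the two rules as a predictor and cannot enter the other.

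Sensitivity is the share of cases that a rule would have selected before diagnosis. A risk score that already contains the diagnosis does not measure that. If cancer history carries a positive weight, the error can move cases only from PLCOm2012-negative to PLCOm2012-positive, which is the direction that the first hypothesis in section B predicts. As far as the printed form shows, item 6 has no field for cancer type or date, so the form alone cannot separate a yes due to the index cancer from a genuine earlier cancer. C13.3 also splits Vancouver participants by the same 1.51% threshold, so a miscoded score would carry into that split.

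**Working it through.** **Which rule is touched.** C5.0 gives the Figure 2 form to cases, item 6 is answered yes by every case if read literally, and the form outputs both results. USPSTF uses age, pack-years and quit time, so its shift through item 6 is zero. PLCOm2012 shifts if item 6 feeds the PLCO index.

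**Inputs from the protocol.** Threshold 1.51%, at the 65th percentile of risk, identifying 80% of ever smokers who will have lung cancer (A1). AUC 0.80 in the PLCO cohort (C13.3). Planned sensitivities in the prospective cohort: 94.3% for PLCOm2012 and 83.8% for USPSTF (C13.1).

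**Assumed, not in the documents.** Odds ratio (OR) for cancer history 1.1 to 2.0. Share h of cases with a genuine earlier cancer 5% to 15%. Log-odds of risk normally distributed among cases.

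**Step 1: reproduce the protocol's 80%.** In a binormal model, s = √2 × z(0.80) = 1.190. Sensitivity at the 65th percentile = Φ(s − z(0.65)) = Φ(1.190 − 0.385) = Φ(0.805) = 79%, close to the stated 80%. The model is therefore a fair scale for an illustration.

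**Step 2: effective cut-off for a false yes.** A false yes adds ln(OR) to the log-odds, so the 1.51% cut-off acts as expit(logit(0.0151) − ln OR). For OR 1.5 the odds are 0.01533 / 1.5 = 0.01022, a risk of 1.01%.

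**Step 3: inflation.** With true sensitivity S, the scored sensitivity among affected cases is S′ = Φ(z(S) + ln(OR)/s). Only the share 1 − h is wrongly scored, so the inflation is (1 − h)(S′ − S). For OR 1.5 and S = 80%: ln(1.5)/1.190 = 0.341, Φ(0.842 + 0.341) = 88.15%, a gain of 8.15 points. Multiplied by 0.85 to 0.95, this is 6.9 to 7.7 points.

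| Assumed OR | Effective cut-off | Inflation, S = 80% (points) | Inflation, S = 94.3% (points) |
|---|---|---|---|
| 1.1 | 1.37% | 1.8 to 2.1 | 0.7 to 0.8 |
| 1.2 | 1.26% | 3.4 to 3.8 | 1.3 to 1.5 |
| 1.5 | 1.01% | 6.9 to 7.7 | 2.5 to 2.8 |
| 2.0 | 0.76% | 10.4 to 11.7 | 3.5 to 4.0 |

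Letting the SD of log-odds run from 1.0 to 1.5 instead of 1.190 widens the ranges to 1.5 to 13.1 points (S = 80%) and 0.6 to 4.3 points (S = 94.3%).

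**The case against.** **The link is inferred.** The protocol does not list the PLCOm2012 variables, so a reader might take it as stated that item 6 enters the score. It is not stated. It is a strong inference: the form produces the PLCO index, the model has seven non-smoking variables, and C12 names personal cancer history as an important predictor in discussing the PLCO models. The positive sign of its weight is likewise assumed.

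**Staff may code it sensibly.** Interviewers might ignore the index cancer, or a data manual might say so. That is possible, but the protocol names this form and this use without any such rule. Unwritten practice could also differ between interviewers.

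**The size is unknown.** This stands. At OR 1.1 the effect is about 2 points or less on either anchor. A reader might compare the inflation with the 10.5-point gap in C13.1 (94.3% − 83.8%) and conclude that the artefact could explain half to nearly all of it. That mixes two anchors. With OR 1.3 to 1.8 and h of 10% to 15%, the gain is 4.9 to 10.2 points from a base of 79%, but only 1.8 to 3.4 points from the 94.3% on which that gap rests, or 17% to 33% of it. C13.1 also describes a prospectively followed cohort, and C5.0 states no expected gap of its own.

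**The reach is narrow.** This also stands. C5.0 is headed as optional. A reader might infer that the main comparison is compromised, but Study Plan 3.2 and C13.1 score risk before diagnosis, where this error cannot arise. Nor are the case data lost for the C12 question of which earlier cancers matter: C12 uses a separate detailed questionnaire that covers personal cancer history, and C5.0 gives Appendix 1 to the same patients.

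**Conclusion.** The point holds for C5.0 and Study Plan 3.1. Used as printed, the form makes the cancer under study count as cancer history for every case, which favours PLCOm2012 and leaves USPSTF unchanged. The direction rests on two conditions: item 6 feeds the PLCO index, and its weight is positive. The size is illustrative only: roughly 2 to 12 points at a true sensitivity of about 80%, and roughly 1 to 4 points at 94.3%, for assumed odds ratios of 1.1 to 2.0. The documents cannot show which part of these ranges applies. They support neither a claim about the powered prospective comparison nor a claim that the error accounts for a given share of the C13.1 difference. The error can be corrected after the fact from other records, but it should be closed off in the protocol, because the comparison is a listed study plan item and the bias runs with the hypothesis.

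**What to change.** - In C5.0, state that for newly diagnosed patients item 6 refers to cancers diagnosed before the present lung cancer, and that this answer is the one entered in the tool. A possible wording: Before your present lung cancer, had you ever been diagnosed with any cancer? The existing skin cancer exception stays.
- For forms already completed, recode item 6 from the cancer agency record or the detailed questionnaire, and rescore.
- Leave patients with an earlier lung cancer out of the relative-sensitivity comparison, since C2.2 excludes them from screening.

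The cost is one reworded question, a recode of any completed forms, and a reported PLCOm2012 sensitivity that may be lower. The prospective cohort needs no change.
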